9.2 Sample Size and Randomization

Power consideration for Aim 1:

Based on past findings, we expect that Mindfulness Training (MT) and Spinal Manipulation Therapy (SMT) will have near-equivalent effects on the primary outcome, changes in EO function. We ran power calculations assuming a true difference of 0 between MT and SMT. Please note that we plan to enroll 286 participants to achieve a sample size of 240 completed participants. See below:

Power Analysis of Two-Sample T-Test for Testing Equivalence Using Differences

Power	MT	SMT	Lower	Upper	True Difference	Standard Deviation	Alpha	Beta
	Group	Group						
	Sample Size (N1)	Sample Size (N2)	Lower	Upper	True Difference	Standard Deviation	Alpha	Beta
0.851	120	120	-3.0	3.0	0.0	7.5	0.050	0.149
0.950	120	120	-3.5	3.5	0.0	7.5	0.050	0.050
0.987	120	120	-4.0	4.0	0.0	7.5	0.050	0.013

An equivalence test of means using two one-sided tests on data from a parallel-group design with sample sizes of 120 in the reference group and 120 in the treatment group achieves 85% power at a 5% significance level when the true difference between the means is 0.0, the standard deviation is 7.5, and the equivalence limits are -3.0 and 3.

Power considerations for Aim 2:

We will test effects of MT and SMT on the treatment-specific mechanisms, pre-post treatment changes in mindfulness and spinal stiffness. Per reviewer suggestions and input from our co-I, [name], we expanded the assessment of “mindfulness” to include pain unpleasantness/bothersome ratings and the Multidimensional Assessment of Interoceptive Awareness (MAIA) scale as well as the Five Facets of Mindfulness Questionnaire (FFMQ). We expect MT to produce larger changes in the mindfulness measures than SMT, and for SMT to produce larger changes in spinal stiffness than MT.

Null Hypothesis: Mean1=Mean2. Alternative Hypothesis: Mean1 \neq Mean2

Allocation

Power	N1	N2	Ratio	Alpha	Beta	Mean1	Mean2	S1	S2
0.800	120	120	1.0	0.050	0.200	0.36	0.00	1.00	1.00
0.983	120	120	1.0	0.050	0.017	0.53	0.00	1.00	1.00

Treatment group sample sizes of 120 and 120 will achieve 80% power to detect a difference of Cohen's $d = 0.36$. With a larger effect – $d = .53$ -- at $\alpha=0.05$ we will have 98.3% power to detect a treatment difference.

Power considerations for Aim 3:

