The first focus is to determine whether pre-post changes in specific and non-specific mechanisms (e.g., specific: spinal stiffness changes; non-specific: self-efficacy changes) interact with Treatment Condition to predict pre-post changes in DVs (e.g. pain intensity changes). A significant interaction would suggest that pre-post changes in a mechanism factor predicted pre-post changes in a DV **differently** depending on Treatment Condition. In the case of a significant interaction, we will test simple slopes of pre-post mechanism changes for DV changes for each Treatment Condition separately. We do not expect many significant interactions. Thus, we focus our power analyses on detecting increments in R^2 when adding pre-post mechanism change scores into regressions to predict pre-post changes in outcomes.

Multiple Regression Power Analysis

Power	N of independent variables teste	R ² for Independent Variable(s) tested	R ² for Variables controlled
0.74152	1	0.025	0.1
0.81731	1	0.030	0.1
0.79137	1	0.025	0.2
0.86115	1	0.030	0.2
0.84360	1	0.025	0.3
0.90403	1	0.030	0.3

All calculations assume $N=240$ and $\alpha=0.05$. Again note that we expect to recruit 286 subjects to achieve an analyzable sample of 240 completed subjects.

With 10% of variance in pre-post outcome changes accounted by mechanism variables already in the equation, we have 74% power to detect a 2.5% increment in R^2 with the addition of another mechanism variable. This increases to 90% power to detect a 3% increment in R^2 when mechanism variables already in the equation account for 30% of the outcome changes. Note that these power analyses for Aim 3 were based on testing the association between changes in EO function and changes in pain interference.

Treatment Assignment Procedures

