Candidate covariance structures will be assessed using the data's correlation structure and Akaike's Information Criterion (AIC). Random coefficients (e.g. random intercept and/or random slope) will be included in the model if they significantly improve the model fit as determined by the likelihood ratio test. Standardized residuals and Cook's distance will be used to assess the influence of outliers and individual observations. Residual plots will be used to check the multivariate normal distribution assumption. The pattern of missing data will be examined to determine its

missing mechanism and the amount. If data are missing not at random (MNAR), data imputations may be used. If other deviations from the model assumptions are detected, appropriate measures will be taken to prevent inferential bias, e.g. data transformations and use of bootstrap techniques to compute standard errors.

Potential covariates (site, age, and any baseline variables found to be significantly different ($p < .20$) between treatment groups) will be considered for model inclusion using a model selection method called least absolute shrinkage and selection operator (LASSO) (Tibshirani, 2011). This method identifies groups of covariates to form a parsimonious model; it avoids problems in stepwise procedures such as collinearity, bias, and variance deflation (Flom & Cassell, 2007); the method has recently been extended to mixed effects models (Bondell, Krishna, & Ghosh, 2010; Fan & Li, 2012; Fernandez, 2007).

Aim 3: To test the relative predictive validity of non-specific and specific mechanisms.

To test to what degree changes in non-specific and specific mechanisms predict changes in pain, mood and function, and whether these relationships depend on the treatment received, we will first test Mechanism x Treatment interactions to determine whether changes in any of the candidate mechanisms predict outcomes to a greater degree in one treatment over the other. Linear mixed effects regression models will be conducted to test, for example, a non-specific mechanism change score x Treatment interaction for each outcome change. If significant differences are observed, then the interaction effects will be interpreted to provide the unique effect of mechanism change for each treatment group.

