In the absence of interactions, we will use linear mixed effects regression models to test the degree to which changes in non-specific and specific mechanisms account for unique and shared variance in pre-post outcome changes. More specifically, 0-order correlations among mechanism and outcome pre-post change scores will reveal “candidate” mechanisms (i.e., those with significant associations with pre-post outcome changes). We will use a series of hierarchical regressions to examine the degree to which ostensibly different mechanisms account for shared or unique variance in outcome changes. Such analyses will allow us to identify common areas of mechanism overlap (e.g., changes in self-efficacy and pain catastrophizing accounting for much shared variance in pain changes), and mechanism uniqueness (e.g., changes in spinal stiffness accounting for significant unique variance in pain changes even with other mechanism changes controlled).

Aim 4: Address competing causation pathways.

First, we will use an approach and techniques that we have used in previous publications [eg, [name], J.W., Nielson, W.R., Jensen, M.P., Heapy, A., Czlapinski, R., & Kerns, R.D. (2015). Specific and general therapeutic mechanisms in cognitive-behavioral treatment of chronic pain. *Journal of Consulting and Clinical Psychology*. 83, 1-11. PMID: 24979313]. Namely, we will test lagged and cross-

lagged effects using pre- to mid-treatment and mid- to post-treatment epochs. Given that endogenous opioid functioning will be assessed only at pre-and post-treatment, and given that the working alliance and subject expectations for benefit will be assessed only at 3- and 6-weeks, this approach will allow to examine comparable effects across all our specific and non-specific mechanisms. Residual change scores for all mechanism and outcome variables will be computed by regressing mid-treatment on pre-treatment values (i.e., a pre-mid residual change score), and regressing post-treatment on mid-treatment values (i.e., mid-post residual change score). For lagged relationships, regressions will be performed to identify the unique effect of pre-mid mechanism changes on mid-post outcome changes. This will require statistically controlling for the path from pre-mid mechanism change to mid-post mechanism change and pre-mid outcome change to mid-post outcome change. See Figure 1 and 2 below. The red line is the target lagged effect. The two blue lines are the paths to be controlled.

Figure 1

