[figure not shown]
[figure not shown]

Figure 2

For cross-lagged effects, the procedure will be inverted. Namely, we will test whether pre-mid changes in outcomes predict mid-post changes in mechanisms. Significant lagged effects paired with non-significant cross-lagged effects will add support to the notion that early-treatment changes in putative mechanisms influenced later-treatment changes in outcomes. In general, we expect that pre-mid changes in mindfulness and spinal stiffness will predict mid-post changes in pain interference (and other outcomes), but the inverse will not be the case.

Second, we will take a more fine-grained HLM approach using the weekly data. We will test whether: a) previous week levels of specific (e.g., mindfulness, spinal stiffness) and nonspecific mechanisms (e.g. self-efficacy) predict previous week to next week changes in outcomes; b) these relationships depend on time in treatment (i.e. quadratic trends could emerge indicating that early- vs late-treatment effects are distinct); c) whether the inverse relationships (i.e. outcomes predicting mechanisms) are also significant; d) whether patterns of lagged effects are different between MT and SMT. In general, we expect that previous week levels in mechanisms will predict previous week to current week changes in outcomes, and that the strength of these relationships will be strongest from Week 3 to Week 6 (when specific mechanisms have improved sufficiently to best affect improvements in outcomes).

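### The pooled Aim 3 analyses and the three-wave Aim 4 regressions do not name treatment arm among the adjusted terms, so associations for mindfulness and spinal stiffness can be partly confounded by arm

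*Protocol*

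**What the plan says.** Protocol Section 9.6 analyses Aim 3 in two steps. Arm enters the first, which asks whether a mechanism is a stronger predictor under MT or under SMT: "we will first test Mechanism x Treatment interactions to determine whether changes in any of the candidate mechanisms predict outcomes to a greater degree". The second step, on how much outcome variance the mechanisms explain, pools the arms: "In the absence of interactions, we will use linear mixed effects regression models to test the degree to which changes in non-specific and specific mechanisms". Its candidates are picked by an unadjusted screen: "0-order correlations among mechanism and outcome pre-post change scores will reveal". The modelling that follows is described thus: "We will use a series of hierarchical regressions to examine the degree to which ostensibly different mechanisms account for shared or unique variance". No arm term is named in this second step. The Aim 3 power text in Section 9.2, for a 2.5% increment in R², describes the background model in the same way: "With 10% of variance in pre-post outcome changes accounted by mechanism variables already in the equation, we have 74% power". It also anticipates few significant interactions, so the pooled step is the expected main route for Aim 3.

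For Aim 4, the pre/mid/post regressions must control two paths: early to late mechanism change, and early to late outcome change. The text on the figures says "The two blue lines are the paths to be controlled". Arm is not mentioned. The weekly HLM analysis, by contrast, does compare lagged patterns between MT and SMT.

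On the mechanisms themselves, Section 9.2 says "We expect MT to produce larger changes in the mindfulness measures than SMT", with the reverse for spinal stiffness, and shows power at d = 0.36 and d = 0.53. These are the mechanisms singled out for Aim 4: "we expect that pre-mid changes in mindfulness and spinal stiffness will predict mid-post changes in pain interference".

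**The concern.** A change score that differs systematically by arm carries information about which arm the patient was in. If outcome change also differs by arm through some other route, a pooled model without arm turns that difference into a mechanism-outcome association, even when none exists inside either arm. A non-significant interaction does not protect against this. It says only that equal slopes were not rejected, and gives no reason to drop the arm main effect.

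Mindfulness is expected to favour MT and stiffness to favour SMT, so the distortion would run in opposite directions for the two. It would raise the apparent value of the mechanism belonging to the arm with the better outcomes and lower that of the other. Aim 3 is meant to compare the predictive value of mechanisms, so a distortion of the comparison matters even when it is small.

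**Working it through.** **Inputs.** N = 240, alpha = 0.05, and mechanism differences d_M = 0.36 and 0.53, all from Section 9.2. The protocol gives no arm difference in outcome, so d_Y = 0, 0.2, 0.5 and 0.8 SD are assumptions.

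**The plan's own figures.** For an R² increment, f² = R²_test / (1 − R²_control − R²_test) and λ = N·f². With 1 variable tested and 1 controlled, the degrees of freedom are 1 and 237. For the first row of the table, f² = 0.025/0.875 = 0.0286 and λ = 6.86, giving power 0.74152. All six stated powers reproduce to five decimals.

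**Zero-order screen, no within-arm association.** With equal arms, the correlation of arm with a variable is d/√(d² + 4).
- Arm with mechanism: 0.36/√4.1296 = 0.177, and 0.53/√4.2809 = 0.256.
- Arm with outcome: 0.2/√4.04 = 0.0995, 0.5/√4.25 = 0.243, and 0.8/√4.64 = 0.371.

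The spurious pooled correlation is the product of the two. Its rejection rate comes from the noncentral F on 1 and 238 degrees of freedom with λ = 240·r²/(1 − r²).

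| Assumed d_Y | d_M = 0.36: r, rejection rate | d_M = 0.53: r, rejection rate |
|---|---|---|
| 0 | 0, 5% | 0, 5% |
| 0.2 | 0.018, 5.9% | 0.025, 6.8% |
| 0.5 | 0.043, 10.2% | 0.062, 16.1% |
| 0.8 | 0.066, 17.4% | 0.095, 31.4% |

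**How much of the arm effect is absorbed.** The spurious R² is the product of the two squared correlations. The mechanism therefore takes up 0.177² = 3.1% or 0.256² = 6.6% of the outcome variance that arm explains. The largest spurious R² in the table is 0.095² = 0.009, below the 0.025 increment in the power table.

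**The opposite direction.** Suppose there is a true within-arm slope but the total outcome difference between arms is zero. The pooled slope is then the within-arm slope divided by (1 + d_M²/4): 1/1.0324 = 0.97 and 1/1.0702 = 0.93 of its value.

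**Three-wave Aim 4 model.** This was simulated with 2,000 runs per case and no within-arm link. The assumptions were autocorrelation 0.6, the mechanism difference complete by mid-treatment, and half the outcome difference present at mid and all of it at post.

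| Assumed d_Y | Without arm, d_M = 0.36 | Without arm, d_M = 0.53 |
|---|---|---|
| 0 | 5.3% | 4.8% |
| 0.2 | 5.3% | 7.0% |
| 0.5 | 10.0% | 17.5% |
| 0.8 | 17.6% | 32.9% |

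With arm added, every case returned to 4.4-5.6%.

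**Cost of adding arm.** With the R² inputs unchanged, one more controlled variable moves power from 0.74152 to 0.74150 and from 0.90403 to 0.90402. Collinearity raises the variance of the mechanism slope by 1/(1 − 0.031) = 1.03 or 1/(1 − 0.066) = 1.07.

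**The case against.** The strongest case against has four parts.

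1. **Part of the omission is silence.** Section 9.6 does not list the blocks of the hierarchical regressions, and a separate analysis plan could add arm. The Aim 4 text states what must be controlled without saying that nothing else may be, its figures are not available here, and it refers to a previously published approach. This stands for the hierarchical regressions and, in part, for Aim 4. It does not stand for the screen, since a zero-order correlation is unadjusted by definition.

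2. **The protocol expects the condition that removes the inflation.** Section 3 expects similar overall outcomes in the two arms, and Section 9.5 examines the arm effect on outcome before the multivariable work. The first point limits the likely size. The second shows whether there is an arm difference but does not adjust for it.

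3. **Other safeguards exist.** Section 3 asks that a specific mechanism predict outcome only in the relevant treatment, and arm appears in the interaction step and the weekly HLM. These reduce the risk of a false claim of specificity. They do not correct the pooled estimates of unique and shared variance.

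4. **The main results are not touched.** The primary mechanism outcome is EO function (Sections 1.1 and 9.5.1), a non-specific mechanism expected to change almost equally in both arms. The Aim 3 power calculation was built on EO function and pain interference. This stands: the Aim 2 argument reaches only mindfulness and spinal stiffness, which are secondary (Section 9.5.2).

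A reader might also infer that the whole of any arm difference in outcome would be credited to the mechanism. The arithmetic does not support that: only the part shared with the mechanism is absorbed, and the bias can also run against a real association. Nor does the protocol support much larger error rates. A rate of 39% needs a mechanism difference of 1.0 SD with an outcome difference of 0.5 SD, and the protocol gives no such mechanism difference.

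**Conclusion.** The point holds for the two specific mechanisms. As written, the Aim 3 screen is unadjusted, and neither the pooled Aim 3 regressions nor the three-wave Aim 4 regressions name arm, although Aim 2 expects these mechanisms to differ by arm. At d = 0.36 the 5% screen would reject about 6-10% of the time, and at d = 0.53 about 7-16%, for an assumed outcome difference of 0.2-0.5 SD with no within-arm association. The Aim 4 figures are similar but depend on the simulation assumptions. With equal outcomes there is no inflation, and a true slope would be diluted only to about 0.97 or 0.93. This is a modest, conditional bias in secondary analyses. It is worth removing because doing so is nearly free; it is not a threat to the primary objective.

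**What to change.** Keep the MT/SMT main effect as a fixed term in the pooled Aim 3 regressions after the interaction is dropped, and in both the lagged and the cross-lagged three-wave Aim 4 regressions. Replace the zero-order screen with correlations partialled for arm, or equivalently with change scores centred within arm. Using one rule for all mechanisms keeps the comparison of unique and shared variance on a common footing, although the need arises for mindfulness and stiffness.

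The cost is one degree of freedom per model and the small collinearity loss shown above. No new data or visits are needed. If an arm difference in outcome runs entirely through the mechanism, the adjusted model still estimates the same slope, only slightly less precisely.

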1.2 Secondary Objectives

A secondary objective is to examine the degree to which MT and SMT exert effects on the other non-specific mechanisms: CPM, pain-related cognitions, the working alliance and patient expectations. Hypothesis 2: MT and SMT will produce near equivalent effects on these non-specific mechanisms.

Another secondary objective is to test the effects of MT and SMT on specific mechanisms. We will test to what degree MT and SMT produce changes in treatment-specific mechanisms (MT: changes in how patients think about pain; SMT: spinal stiffness). Hypothesis 2: MT and SMT will each affect their own treatment-specific mechanism more than will the other treatment (e.g., MT will produce larger changes in mindfulness than SMT; SMT will produce larger changes in spinal stiffness than MT).

A third secondary objective is to test the relative predictive validity of non-specific and specific mechanisms. We will test to what degree changes in non-specific and

specific mechanisms predict changes in pain, mood and function, and whether these relationships depend on the treatment received. We will first test Mechanism Change x Treatment interactions to determine whether changes in any candidate mechanisms predict outcomes to a greater degree in one treatment than the other. In the absence of interactions, we will test the degree to which changes in non-specific and specific mechanisms account for unique and shared variance in predicting outcomes.

A final secondary objective is to examine competing causation paths. We will test lagged effects of early-treatment changes in specific and non-specific mechanisms on predicting late-treatment changes in outcomes, and vice versa.

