Aim 3: Test relative predictive validity of non-specific and specific mechanisms. We will test to what degree changes in non-specific and specific mechanisms predict changes in pain, mood and function, and whether these relationships depend on the treatment received. We will first test Mechanism Change x Treatment interactions to determine whether changes in any candidate mechanisms predict outcomes to a greater degree in one treatment than the other. In the absence of interactions, we will test the degree to which changes in non-specific and specific mechanisms account for unique and shared variance in predicting outcomes.

Aim 4: To address competing causation paths, we will test lagged and cross-lagged effects of early-treatment changes in non-specific and specific mechanisms predicting late-treatment changes in outcomes.

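### Aim 4 reads causal direction from a significant lagged path beside a non-significant reverse path, but non-significance does not show that the reverse path is absent or smaller

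*Protocol*

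**What the plan says.** Section 1.2 gives the purpose: "A final secondary objective is to examine competing causation paths". Section 9.1 repeats it for Aim 4: "To address competing causation paths, we will test lagged and cross-lagged effects of early-treatment changes".

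Section 9.6 sets out two approaches.

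- **Two-epoch residual change scores.** For the forward path, "regressions will be performed to identify the unique effect of pre-mid mechanism changes on mid-post outcome changes", with two other paths controlled. For the reverse path the procedure is inverted: "Namely, we will test whether pre-mid changes in outcomes predict mid-post changes in mechanisms". The reading rule follows: "Significant lagged effects paired with non-significant cross-lagged effects will add support to the notion" that early mechanism change influenced later outcome change. The stated expectation is that early changes in mindfulness and stiffness "will predict mid-post changes in pain interference (and other outcomes), but the inverse will not be the case".
- **Weekly multilevel models.** Among other questions, these ask "whether the inverse relationships (i.e. outcomes predicting mechanisms) are also significant" and "whether patterns of lagged effects are different between MT and SMT". The second of these compares treatments, not directions.

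The protocol states no test or interval for the difference between the two directional paths, no bound below which the reverse path would count as negligible, and no power or effect size for Aim 4.

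**The concern.** The rule uses the contrast between a significant and a non-significant result as evidence about direction. Two coefficients can fall on opposite sides of the 5% line when their true values are the same. The reverse path can be missed simply because its test lacks power. To say that influence runs from mechanism to outcome rather than back, one needs an estimate of how the paths differ, or an interval showing that the reverse path is small. The plan asks for neither.

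The rule would be applied to several mechanisms and to outcomes beyond pain interference, so there are many opportunities for a one-sided pattern to arise by chance. Because the protocol itself fixes this reading, it is more than a detail left for a SAP to fill in.

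**Working it through.** **Inputs from the protocol.** Section 9.2, power for Aim 3: N = 240, alpha = 0.05, increments in R² of 0.025 or 0.030, and R² for controlled variables of 0.1, 0.2 or 0.3. The printed power runs from 0.74152 to 0.90403. There is no Aim 4 power statement, so this is the nearest stated figure for one regression term.

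**Step 1: reproduce the stated power.** Use f² = ΔR² / (1 − R²controlled − ΔR²) and noncentrality λ = N × f², with 1 and 237 degrees of freedom (one control variable).

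- Lowest row: f² = 0.025 / 0.875 = 0.02857; λ = 240 × 0.02857 = 6.857; power = 0.74152.
- Highest row: f² = 0.030 / 0.670 = 0.04478; λ = 240 × 0.04478 = 10.746; power = 0.90403.

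All six printed values reproduce to five decimals.

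**Step 2: how often the rule gives a one-sided pattern when the paths are equal.** Assume that both true paths are equal and non-zero, that each test has power p, and that the tests are independent. Then P(forward significant, reverse not) = p(1 − p), and P(exactly one significant) = 2p(1 − p).

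| Power p | Source of p | Mechanism-first pattern | One-sided, either direction |
|---|---|---|---|
| 0.904 | section 9.2 | 8.7% | 17.4% |
| 0.817 | section 9.2 | 14.9% | 29.9% |
| 0.742 | section 9.2 | 19.2% | 38.3% |
| 0.70 | assumed | 21% | 42% |
| 0.50 | assumed | 25% | 50% |
| 0.30 | assumed | 21% | 42% |

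**Step 3: does this depend on independence?** A two-equation panel was simulated with N = 240 and 6,000 runs per scenario. Stability paths were 0.3, and paths are per standard deviation of the predictor with residual standard deviation 1. A direct Wald test of path difference, using the covariance of the two estimates, was run on the same data. Path sizes and correlations are assumptions.

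| Forward / reverse path | Correlation of predictors and of residuals | Mechanism-first pattern | Difference test significant (two-sided) |
|---|---|---|---|
| 0.10 / 0.10 | 0.3 | 23.0% | 5.3% |
| 0.135 / 0.135 | 0.3 | 26.5% | 5.0% |
| 0.18 / 0.18 | 0.3 | 20.0% | 4.8% |
| 0.18 / 0.18 | 0 | 17.6% | 5.1% |
| 0.18 / 0.18 | 0.5 | 25.1% | 4.5% |
| 0.18 / 0.10 | 0.3 | 53.1% | 12.6% |
| 0.18 / 0 | 0.3 | 70.8% | 43.3% |

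With equal paths the pattern appears in 18% to 27% of simulated trials. The difference test is significant in about 5%, so in about 2.5% in favour of the mechanism.

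**Step 4: the case where no forward path exists.** If both paths are zero and the tests are independent, the pattern occurs in 0.05 × 0.95 = 4.75% of trials. If only the reverse path exists, it occurs in 0.05 × (1 − p), which is 1.3% at p = 0.742 and 0.5% at p = 0.904.

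**The case against.** The strongest reply is that the protocol's sentence claims only that mechanisms influenced outcomes. With equal non-zero paths that claim is true, so the percentages in Step 2 are not false conclusions about it. This stands. A reader might infer that the rule finds a causal direction where no effect exists. Step 4 shows otherwise: with no forward path the pattern appears in under 5% of trials. The figures apply only to the further inference that the reverse path is absent or weaker. That inference is nevertheless close at hand, because the aim is to settle competing paths and the next sentence expects the inverse not to hold. That sentence is an expectation, not a decision rule.

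A reader might also take the two-epoch rule to be the sole criterion for direction. It is not, since the weekly models are a second approach. They do not cure the problem, because they too judge the inverse path by significance. The requirement in section 3 that mechanism change precede and predict outcome change only in the relevant treatment concerns treatment specificity, not which way influence runs.

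Power of 30% to 70% cannot be presented as the protocol's own position. It is an assumption, and the figures based on Aim 3 power are lower.

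Finally, the wording is hedged, since the pattern is said to add support and not to prove. Making a difference that excludes zero the sole gate would also be costly: with a truly one-way effect (0.18 against 0) it succeeds in 43% of trials, against 71% for the protocol's pattern. Standardised paths between unlike constructs also depend on how reliably each is measured. These points argue for reporting intervals, not for a new pass/fail rule.

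**Conclusion.** The point holds for inference about the reverse path. Section 9.6 treats a non-significant reverse path as informative about direction, and nothing in the protocol compares the two directions. With equal non-zero paths and independent tests, the mechanism-first pattern appears in 19% down to 9% of trials at the power the protocol gives for one Aim 3 term (0.74 to 0.90), and a one-sided pattern in either direction in 38% down to 17%. At an assumed power of 30% to 70% the figures are 21% to 25% and 42% to 50%. Applying Aim 3 power to Aim 4 is itself an assumption. Correlated tests give results of the same order.

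The documents do not support saying that the rule will often credit mechanisms with an influence they lack. Aim 4 is a secondary objective, and the comparison of endogenous opioid function is untouched. The wording should be changed before analysis, but the trial's main result does not depend on it.

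**What to change.** In section 9.6, Aim 4:

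- For each mechanism-outcome pair, fit the lagged and cross-lagged paths in one model on standardised variables.
- Report each path with its 95% confidence interval.
- Report the difference between the paths with a 95% confidence interval (bootstrap), or test it with an equality constraint.
- Replace the significant/non-significant sentence with an interpretation based on these intervals, and say that a non-significant reverse path will not be read as absent.
- Treat the inverse relationships in the weekly models in the same way.

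No new data or visits are needed. The price is precision: a difference between two paths is estimated less precisely than a single path. In the simulation, power was about 43% for the difference with paths of 0.18 and 0 at N = 240, against about 75% for the forward path alone. Fewer directional statements will be firm, including some that would have been correct.
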